4.1.3 Investigational Drug MK-3475 (Pembrolizumab)

Pembrolizumab will be available in 100mg solution in a single use-vial for intravenous administration.

Classification

Antineoplastic

Mechanism of Action

Pembrolizumab (previously known as SCH 900475) is a potent and highly selective humanized monoclonal antibody (mAb) of the IgG4/kappa isotype designed to directly block the interaction between PD-1 and its ligands, PD-L1 and PD-L2. This blockade enhances functional activity of the target lymphocytes to facilitate tumor regression and ultimately immune rejection.

Contraindications

None

Availability

Pembrolizumab is an investigational agent supplied by Merck, for storage and application please refer to lab manual.

Summary

The programmed cell death 1 (PD-1) pathway represents a major immune control switch which may be engaged by tumor cells to overcome active T-cell immune surveillance.

MK-3475 (Pembrolizumab, previously known as SCH 900475) is a potent and highly selective humanized monoclonal antibody (mAb) of the IgG4/kappa isotype designed to directly block the interaction between PD-1 and its ligands, PD-L1 and PD-L2. This blockade enhances functional activity of the target lymphocytes to facilitate tumor regression and ultimately immune rejection.

Merck is studying pembrolizumab for various oncology indications. An open-label Phase I study is being conducted to evaluate the safety and clinical activity of pembrolizumab when administered as monotherapy. The dose escalation portion of this study evaluated three dose levels of single agent pembrolizumab (1 mg/kg, 3 mg/kg, and 10 mg/kg), in patients with advanced solid tumors. All three dose levels were well tolerated and no dose-limiting toxicities (DLTs) were observed, therefore the maximum tolerated dose (MTD) has not been determined. The ongoing expansion part of this study is evaluating pembrolizumab in patients with melanoma (MEL) and non-small cell lung cancer (NSCLC).

In a Phase II study, is also being conducted to evaluate the safety and clinical activity of pembrolizumab relative to standard of care chemotherapy in melanoma.

In a randomized, controlled, open-label, three-arm Phase III pivotal study is being conducted to evaluate two dosing regimens of pembrolizumab versus ipilimumab (IPI) in patients with unresectable or metastatic MEL who have not received IPI treatment. Protocol 010 (PN010), a randomized, adaptively designed Phase II/III trial is being conducted to evaluate two dosing schedules of pembrolizumab (10 mg/kg Q3W or 2 mg/kg Q3W) versus docetaxel in patients with NSCLC with PD-L1 positive tumors who have experienced disease progression after platinum-containing systemic therapy.

In an open-label, non-randomized, Phase I study is evaluating pembrolizumab alone in Japanese patients with advanced solid tumors and in combination with cisplatin/pemetrexed and carboplatin/paclitaxel in patients with advanced NSCLC. The combination therapy portion of the trial had not yet initiated as of 18-Oct-2013.

In a nonrandomized, multi-cohort trial is evaluating pembrolizumab 10 mg/kg Q2W in patients with PD-L1 positive advanced solid tumors. Cohort A is enrolling patients with triple negative breast cancer, Cohort B is enrolling patients with squamous cell carcinoma of the head and neck, Cohort C is enrolling patients with urothelial tract cancer of the renal pelvis, ureter, bladder, or urethra. As of the cut-off date of 18-Oct-2013, Cohort D which will enroll patients with adenocarcinoma of the stomach or gastroesophageal junction had not yet initiated. Safety data are continuing to accumulate in the clinical development program across multiple indications; immune-related adverse events (irAEs) are expected based on the nature of the compound, its mechanism of action and reported experience with immunotherapies that have a similar mechanism of action.

Nonclinical Pharmacology

Pembrolizumab strongly enhances T-lymphocyte immune responses in cultured blood cells from healthy human donors, cancer patients, and primates. In T-cell activation assays using human donor blood cells, the EC50 (concentration where 50% of the maximum effect is achieved) has been ~0.1 to 0.3 nM. In addition to interleukin-2 (IL-2), tumor necrosis factor alpha (TNF α), interferon gamma (IFN γ), and levels of other cytokines were modulated by pembrolizumab. The antibody potentiates existing immune responses only in the presence of antigen and does not nonspecifically activate T-cells.

Using an anti-murine PD-1 analog antibody, PD-1 blockade has been shown to significantly inhibit tumor growth in a variety of syngeneic murine tumor models. In these experiments in mice, anti-PD-1 therapy is synergistic with chemotherapeutic agents such as gemcitabine and 5-fluorouracil (5-FU) and combination therapy results in increased complete tumor regression rates in vivo.

Nonclinical Pharmacokinetics

After intravenous (IV) administration of pembrolizumab to cynomolgus monkeys, systemic exposure to pembrolizumab independent of sex, increased with increasing dose. Systemic exposure for the 7-day dosing interval increased after repeated dosing from 40 to 200 mg/kg. Area under the concentration-time curve (AUC) for the 7-day dosing interval (AUC[0-7 days]) after one dose appeared to be dose-proportional from 0.3 to 200 mg/kg, suggesting dose-independent pharmacokinetics (PK). Terminal half-life ($t_{1/2}$) values from individual animals after repeated IV dosing ranged from 11.8 to 23.7 days (mean values ranged from 15.7 to 22.3 days) across the doses tested.

Safety Pharmacology/Toxicology

The potential for systemic toxicity of pembrolizumab was assessed in a 1-month repeat-dose toxicity study with a 4-month recovery in cynomolgus monkeys and in a 6-month repeat dose toxicity study with a 4-month recovery period in cynomolgus monkeys. In the 1-month toxicity study, cynomolgus monkeys were administered an IV dose of 6, 40, or 200 mg/kg once weekly for a total of five doses. Four monkeys/sex/group were euthanized during Week 5. The remaining two monkeys/sex/group were euthanized during Week 23, after a four-month post-dose period. In this study, pembrolizumab was well tolerated in monkeys with the systemic exposure (AUC) up to approximately 170,000 $\mu\text{g}/\text{day}/\text{mL}$ over the course of the study. There was no test article-related mortality, and test article-related changes were limited to an increased incidence of inguinal swelling, and increased splenic weights in males receiving 200 mg/kg. Both of these findings were not considered adverse and there was no histopathologic correlation. Splenic weights were normal at the post-dose necropsy. Anti-pembrolizumab antibodies were detected in seven (out of eight) animals in the 6 mg/kg dose group and one (out of eight) animal in the 40 mg/kg dose group, and were associated with an apparent increase in clearance of pembrolizumab. The presence of anti-drug antibodies (ADA) in monkeys in the low-dose group and in one monkey in the mid-dose group did not impact the pharmacodynamic response as sufficient target engagement was demonstrated for the duration of the study (with the exception of one low-dose monkey). Additionally, anti-pembrolizumab antibodies were not detected in any monkeys in the high-dose group, suggesting that potential toxicity has been evaluated at the highest exposure levels in the study. Based on the lack of adverse test article-related findings in this study, the No Observable Adverse Effect Level (NOAEL) was ≥ 200 mg/kg.

In the 6-month toxicity study, the potential for systemic toxicity was assessed in cynomolgus monkeys administered an IV dose of 6, 40, or 200 mg/kg once every other week for approximately 6 months (a total of 12 doses) followed by a 4-month treatment free period. Three animals/sex/group were designated for interim necropsy at the end of the 6-month dosing phase (3 days after receiving the last dose in Study Week 23); and the remaining monkeys were designated for final necropsy following the 4-month treatment-free period. Pembrolizumab was well tolerated at all dose levels. There were no test article-related antemortem findings. There were no test article-related electrocardiographic or ophthalmic findings. There were no test article-related changes at injection sites. There were no test article-related gross observations or organ weight changes at the interim or final necropsy. Since there were no test article-related histomorphologic findings at interim necropsy, histomorphologic evaluation of tissues collected at final necropsy were not conducted. The presence of ADA was observed in five out of ten animals at 6 mg/kg/dose during the dosing phase, which correlated with an apparent increased rate of elimination of pembrolizumab in these animals. No anti-pembrolizumab antibodies were detected at 40 or 200 mg/kg/dose during the dosing phase, and no MK-3475 serum concentration profiles in these two groups suggested an effect of ADA on pembrolizumab elimination rate. During the treatment-free period, anti-pembrolizumab antibodies were detected in two animals at 6 mg/kg/dose, which already had ADA present during the dosing phase, and in two additional animals (one at 6 mg/kg/dose and one at 200 mg/kg/dose), which were ADA negative during the dosing phase. The detection of anti-pembrolizumab antibodies had a minimal effect on the mean group systemic exposure to pembrolizumab during the study and

did not impact the evaluation of potential toxicity of MK- 3475 for the duration of the 6-month study as there were no test article-related effects on any of the parameters examined and as no monkey in the mid- and high-dose groups developed ADA during the dosing phase. In conclusion, pembrolizumab administered once every other week over a 6-month duration to cynomolgus monkeys was well tolerated and the no observed effect level (NOEL) was ≥ 200 mg/kg/dose (the highest dose tested). In addition, tissue cross-reactivity studies using monkey and human specimens were conducted to evaluate the potential cross reactivity of pembrolizumab with cryosections of cynomolgus monkey tissues and normal human tissues. Results demonstrated the expected on-target staining of the membranes of mononuclear leukocytes in both species. The off-target staining (cytoplasmic and stromal) that occurred in many tissues of both species was considered spurious binding inherent to the experimental conditions of the *in vitro* tissue cross reactivity studies with no *in vivo* toxicological significance.

Clinical Development

Clinical data from PN001 is presented in this report with a visit cut-off date of 26-Jul-2013. As of 26-Jul-2013, there have been 789 patients treated in PN001 with pembrolizumab as a 30-minute IV infusion. Of these 789 patients, preliminary data are presented in this report from 479 patients. Data from 200 patients in Part B3 and 110 patients in Part F that were treated as of the cut-off date were not included in the analyses yet. Based upon this safety database consisting of patients treated up to 10 mg/kg once every two to three weeks, pembrolizumab has been generally well-tolerated at doses up to 10 mg/kg every other week without DLTs. One (0.002%) patient assayed to date had samples confirmed positive for ADA, but no impact on safety has been observed. Five other clinical studies (PN002, PN006, PN010, PN011, and PN012) are ongoing however preliminary data analyses are not yet available. Important safety findings from these studies will be discussed in Section 5 of this report. For these 5 studies, the number of treated patients indicated in this report is based on a visit cut-off date of 18-Oct-2013 to allow for more mature enrollment data and align with the Development Safety Update Report data cutoff date.

Pembrolizumab PK results have been obtained from PN001 following the first dose at 1, 3 and 10 mg/kg IV of pembrolizumab administered to 17 patients with solid tumors. The observed pharmacokinetic profile of pembrolizumab was typical of other IgG mAbs with a half-life ($t_{1/2}$) of approximately 2 to 3 weeks. There was no indication of dose dependency of half-life in the 3 dose groups and a dose related increase in exposure was observed from 1 to 10 mg/kg. The long half-life supports a dosing interval of every 2 or 3 weeks. Exposure obtained with sparse sampling after dosing melanoma and non-small cell lung cancer (NSCLC) patients at 2 and 10 mg/kg, every 2 or 3 weeks, is consistent with this profile.

As of 18-Oct-2013, PN002 has randomized 497 patients with metastatic melanoma (495 patients were treated) across 3 treatment groups as follows, pembrolizumab 2 mg/kg Q3W, pembrolizumab 10 mg/kg Q3W, and chemotherapy (investigator choice of treatment) in a 1:1:1 ratio. PN006 has randomized 68 IPI-naïve patients with unresectable or metastatic melanoma across the 3 treatment groups: 10 mg/kg Q2W, 10 mg/kg Q3W, and ipilimumab in a 1:1:1 ratio. PN010 has randomized three patients with NSCLC across the 3 treatment groups: 10 mg/kg Q3W, 2 mg/kg Q3W, and docetaxel 75 mg/m² Q3W in a 1:1:1 ratio. In PN011 10 patients have been treated. In PN012, 109 patients have been treated across the three cohorts as of 18-Oct-2013.

4.2 Drug Accountability

The Investigational Pharmacist will manage drug accountability records.

4.3 Drug Ordering

UCSF will obtain pembrolizumab (MK-3475) directly from Merck as study supply.

4.4 Packaging and Labeling of Study Drugs

Drugs will be packaged and labeled per UCSF institutional standards, adhering to applicable local and federal laws.

5 Treatment Plan

5.1 Dosage and Administration

The dose regimen of 200 mg Q3W of pembrolizumab is planned for all urothelial cancer trials. Available PK results in subjects with melanoma, NSCLC, and other solid tumor types support a lack of meaningful difference in PK exposures obtained at a given dose among tumor types. An open-label Phase 1 trial (PN001) in melanoma subjects is being conducted to evaluate the safety and clinical activity of single agent pembrolizumab. The dose escalation portion of this trial evaluated three dose levels, 1 mg/kg, 3 mg/kg, and 10 mg/kg, administered every 2 weeks (Q2W) in subjects with advanced solid tumors. All three dose levels were well tolerated and no dose-limiting toxicities were observed. This first in human study of pembrolizumab showed evidence of target engagement and objective evidence of tumor size reduction at all dose levels (1 mg/kg, 3 mg/kg and 10 mg/kg Q2W). No maximum tolerated dose (MTD) has been identified.

In KEYNOTE-001, two randomized cohort evaluations of melanoma subjects receiving pembrolizumab at a dose of 2 mg/kg versus 10 mg/kg Q3W have been completed. The clinical efficacy and safety data demonstrate a lack of clinically important differences in efficacy response or safety profile at these doses. For example, in Cohort B2, advanced melanoma subjects who had received prior ipilimumab therapy were randomized to receive pembrolizumab at 2 mg/kg versus 10 mg/kg Q3W. The overall response rate (ORR) was 26% (21/81) in the 2mg/kg group and 26% (25/79) in the 10 mg/kg group (full analysis set (FAS)). The proportion of subjects with drug-related adverse events (AEs), grade 3-5 drug-related AEs, serious drug-related AEs, death or discontinuation due to an AE was comparable between groups or lower in the 10 mg/kg group.

Available pharmacokinetic results in subjects with melanoma, NSCLC, and other solid tumor types support a lack of meaningful difference in pharmacokinetic exposures obtained at a given dose among tumor types. Population PK analysis has been performed and has confirmed the expectation that intrinsic factors do not affect exposure to pembrolizumab to a clinically meaningful extent. Taken together, these data support the use of lower doses (with similar exposure to 2 mg/kg Q3W) in all solid tumor indications. 2 mg/kg Q3W is being evaluated in NSCLC in PN001, Cohort F30 and PN010, and 200 mg Q3W is being evaluated in head and neck cancer in PN012, which are expected to provide additional data supporting the dose selection.

Selection of 200 mg as the appropriate dose for a switch to fixed dosing is based on simulation results indicating that 200 mg will provide exposures that are reasonably consistent with those obtained with 2 mg/kg dose and importantly will maintain individual patient exposures within the exposure range established in melanoma as associated with maximal clinical response. A population PK model, which characterized the influence of body weight and other patient covariates on exposure, has been developed using available data from 476 subjects from PN001. The distribution of exposures from the 200 mg fixed dose are predicted to considerably overlap those obtained with the 2 mg/kg dose, with some tendency for individual values to range slightly higher with the 200 mg fixed dose. The slight increase in PK variability predicted for the fixed dose relative to weight-based dosing is not expected to be clinically important given that the range of individual exposures is well contained within the range of exposures shown in the melanoma studies of 2 and 10 mg/kg to provide similar efficacy and safety. The population PK

evaluation revealed that there was no significant impact of tumor burden on exposure. In addition, exposure was similar between the NSCLC and melanoma indications. Therefore, there are no anticipated changes in exposure between different tumor types and indication settings.

Table 5.1 Regimen Description

Arm A (Figure 1)

Study Drug	Dose	Route	Schedule	Cycle Length
Tamoxifen	20 mg Tablets	Oral	daily continuous All cycles	3 weeks (21 days)
Vorinostat	400 mg	Oral	Days 5/7 All cycles	
Pembrolizumab	200 mg	Intravenous	Day 1, week 1 Cycles 1+	

Arm B (Figure 1)

Study Drug	Dose	Route	Schedule	Cycle Length
Tamoxifen	20mg Tablets	Oral	daily continuous All cycles	3 weeks (21 days)
Vorinostat	400mg	Oral	Days 5/7 All cycles	
Pembrolizumab	200mg	Intravenous	Day 1, week 1 Cycles 2+	

Arm C (Figure 1)

Study Drug	Dose	Route	Schedule	Cycle Length
Vorinostat	400 mg	Oral	Days 5/7 All cycles	3 weeks (21 days)
Pembrolizumab	200 mg	Intravenous	Day 1, week 1 Cycles 1+	

5.1.1 Dose Modifications and Dosing Delays

The following dose modification rules will be used with respect to potential toxicity. Toxicity will be assessed continuously according to the NCI Common Terminology Criteria for Adverse Events [Version 4.0 \(CTCAE v4.0\)](#)

The following dose modifications should be made for febrile neutropenia, and blood counts obtained on day one of each cycle. If more than one of these conditions applies, use the most stringent (i.e., the greatest dose reduction). **The AE may be due to pembrolizumab or**

vorinostat alone in which case the respective agent should be reduced. If overlapping toxicity is suspected both drugs may be reduced with the potential to re-escalate the non-offending agent. Given the very different nature of pembrolizumab and vorinostat/tamoxifen toxicities, separate tables are shown for individual agents.

No dose modification will be pursued for tamoxifen.

5.1.1.1 Dose Modifications and Dosing Delays Tables for Drug Related Adverse Events

Hematologic toxicity

Neutropenia:

Neutropenia	Vorinostat	Tamoxifen
Febrile neutropenia		
ANC \geq 1000	100%	100%
ANC: 500-1000	Hold for until \leq grade 2 #, Restart at 75%: 300 mg qd for all subsequent cycles Second occurrence resume at 200 mg qd for all subsequent cycles Third occurrence: remove from study	100%
ANC: 0-500	Hold for until \leq grade 2 or less# Restart at 75%: 300 mg qd for all subsequent cycles Second occurrence resume at 200 mg qd for all subsequent cycles Third occurrence: remove from study	100%

#Patient with a dose delay for more than 3 weeks in the first 2 cycles will need to be replaced for toxicity and efficacy assessments.

Patients who developed a second episode of **febrile neutropenia** despite a dose modification will be removed from study.

Anemia

Hemoglobin	Vorinostat	Tamoxifen
>8 mg/dl	100 %: 400 mg qd	100%

6.5-8 mg/dl	75 %: 300 mg qd	100%
<6.5 mg/dl	50 %: 200 mg qd	100%

An alternative to dose modification would be the use of PRBC transfusion. This is not allowed in cycle one, but may be used at the discretion of the treating physician for subsequent cycles.

Thrombocytopenia

Platelets	Vorinostat	Tamoxifen
>75'000	100 %: 400 mg qd	100%
≤75'000	100 %: 400 mg qd	100%
≤50'000/mm ³	Hold until ≤grade 2 or less Restart at 75%: 300 mg qd for all subsequent cycles Second occurrence resume at 200 mg qd for all subsequent cycles Third occurrence: remove from study_	100%
≤25'000/mm ³	Hold until ≤grade 2 or less Restart at 75%: 300 mg qd for all subsequent cycles Second occurrence resume at 200 mg qd for all subsequent cycles Third occurrence: remove from study	100%

Non-hematological toxicities

Laboratory abnormalities must be clinically relevant and dose and drug related to prompt dose modifications.

Bilirubin	Vorinostat	Tamoxifen
≤1.5 mg/dl	100 %: 400 mg qd	100%
1.6 – 3.0 mg/dl	75 %: 300 mg qd	100%

>3.0 mg/dl	First occurrence: hold until \leq grade 2, 75 %: 300 mg qd Second occurrence: Hold until grade 2 or less, 50 %: 200 mg qd	100%
AST/ALT	Vorinostat	Tamoxifen
\leq 2.5 x ULN	100 %: 400 mg qd	100%
2.5-5 x ULN	First occurrence: 75 %: 300 mg qd Second occurrence: 50 %: 200 mg qd	100%
> 5 x ULN	First occurrence: hold until \leq grade 2, resume at 75 %: 300 mg qd Second occurrence: Hold until grade 2 or less, 50 %: 200 mg qd Third occurrence: remove from study	100%

Hepatic Dysfunction: Any new increase in LFTs should raise the concern to rule out progressive metastatic disease. If the rise is not due to progressive metastatic disease, give the following dose based on lab values obtained on day 1 of each cycle:

Effects on the liver: Tamoxifen has been associated with changes in liver enzyme levels, and on rare occasions, a spectrum of more severe liver abnormalities including fatty liver, cholestasis, hepatitis and hepatic necrosis. A few of these serious cases included fatalities. In most reported cases, the relationship to tamoxifen was uncertain. However, some positive rechallenges and dechallenges have been reported. If grade 3 or 4 liver toxicity is maintained after a temporary stopping of vorinostat, both drugs should be stopped. Any rechallenge should be discussed with the study chair. **If treatment is delayed for more than 3 weeks, contact the Principle Investigator.**

Gastrointestinal Toxicity

Nausea/Vomiting/Dehydration: In this protocol, the routine use of any and all anti-emetics is allowed as clinically appropriate; these include the use of dexamethasone and 5-HT3 receptor antagonists.

Patients should maintain adequate fluid and food intake because vorinostat's dose-limiting toxicities are anorexia, dehydration, diarrhea, and fatigue. In the setting of dysgeusia, popsicles and Gatorade have been found to be useful by some investigators to maintain adequate hydration. Patients should also be encouraged to seek a nutritional consult.

Diarrhea: Treat diarrhea promptly with appropriate supportive care, including loperamide. Instruct patients to begin taking loperamide at the first signs of: 1) poorly formed or loose stool, 2) occurrence of more bowel movements than usual in one day, or 3) unusually high volume of stool. Loperamide should be taken in the following manner: 4 mg at first onset of diarrhea then 2 mg after each unformed stool. The daily dose should not exceed 16 mg. Loperamide should not be taken prophylactically. Advise patients to drink plenty of clear fluids to help prevent dehydration caused by diarrhea. Avoid loperamide if there is the presence of blood or mucus in the stool or if

diarrhea is accompanied by fever. If diarrhea is suspected to be linked to pembrolizumab and is \geq grade 3, hold dose until toxicity resolves to \leq grade 1, then resume at dose given in prior cycle.

Other Non-hematological Toxicities:

Laboratory abnormalities must be clinically relevant and dose and drug related to prompt dose modifications.

Give the following dose based on the worst toxicity encountered during the previous cycle:

Fatigue	Vorinostat	Tamoxifen
Grade 1	100%	100%
Grade 2	Hold until toxicity is \leq grade 1, then resume at dose given in prior cycle.	100%
Grade 3, 4	Hold until toxicity is \leq grade 1, then resume at 75% (or less) of dose given in the prior cycle. If grade 3 toxicity recurs despite dose reduction, decrease to 50 % of initial dose.	100%.

Other	Vorinostat	Tamoxifen
Grade 1	100%	100%
Grade 2	Hold until toxicity is \leq grade 1, then resume at dose given in prior cycle.	100%
Grade 3	Hold until toxicity is \leq grade 1, then resume at 75% (or less) of dose given in the prior cycle. If grade 3 toxicity recurs despite dose reduction, decrease to 50 % of initial dose.	100%
Grade 4	Discontinue protocol therapy.	100%

Vorinostat may be reduced for grade II fatigue, asthenia, weight loss or other constitutional symptoms if deemed in the best interest of the patient.

Effects on the Eye: Ocular disturbances, including corneal changes, decrement in color vision perception, retinal vein thrombosis, and retinopathy has been reported in patients receiving tamoxifen. An increased incidence of cataracts and the need for cataract surgery have been reported in patients receiving tamoxifen. If grade 3 or 4 ocular toxicities occur, both drugs should be stopped. Any rechallenge should be discussed with the study chair.

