7.1.2 Definitions

Evaluable for toxicity

All patients will be evaluable for toxicity from the time of their first treatment with the study drug.

Evaluable for objective response

Only those patients who have measurable disease present at baseline, have received at least one cycle of therapy, and have had their disease re-evaluated will be considered evaluable for response. These patients will have their response classified according to the definitions stated below. (Note: Patients who exhibit objective disease progression prior to the end of Cycle 1 will also be considered evaluable.)

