8.3 Analyses Plans

8.3.1 Analysis Populations

We will conduct an intention-to-treat analysis of efficacy. All patients who were randomized will be evaluated.

For evaluation of safety, we will restrict the arm-specific samples to all patients who have received at least one dose of investigational therapy.

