8.3.2 Evaluation of Efficacy

For each arm objective response rate (ORR) will be defined as the proportion of participants randomized to that arm whose status is SD or better (CR, PR) at 24 weeks' follow-up. In addition to calculating the ORR, we will calculate the corresponding Agresti-Coull interval 95% confidence interval (CI) (Ref: *Agresti, Alan; Coull, Brent A. (1998). "Approximate is better than 'exact' for interval estimation of binomial proportions". The American Statistician 52: 119–126. doi:10.2307/2685469*). If the lower bound of the 95% CI exceeds 10%, we will reject the null

hypothesis that the regimen is ineffective and conclude that it is sufficiently effective to warrant further study.

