8.3.3 Evaluation of Safety

Analyses will be performed for all patients having received at least one dose of study drug. The study will use the NCI CTCAE v4.0.

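### The early-dose-delay replacement footnote is not reconciled with the analysis sets in section 8.3 or with the fixed stage counts of 10 and 29; the effect is probably small and the cure is wording

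*Combined protocol and SAP*

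**What the plan says.** **Replacement rule.** In section 5.1.1.1 the # footnote is attached to the two vorinostat hold cells of the neutropenia table. It says that a patient "with a dose delay for more than 3 weeks in the first 2 cycles will need to be replaced for toxicity and efficacy assessments".

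**Efficacy set.** Section 8.3.1: "We will conduct an intention-to-treat analysis of efficacy. All patients who were randomized will be evaluated". Section 8.3.2 defines ORR over "the proportion of participants randomized to that arm", counting those with stable disease or better at 24 weeks. Its decision rule is "If the lower bound of the 95% CI exceeds 10" percent, the null hypothesis is rejected (Agresti-Coull interval).

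**Safety set.** Section 8.3.1: "For evaluation of safety, we will restrict the arm-specific samples to all patients who have received at least one dose of investigational therapy". Section 8.3.3 repeats it: "Analyses will be performed for all patients having received at least one dose of study drug". Section 7.4 has the same sentence, and section 7.1.2 agrees: "All patients will be evaluable for toxicity from the time of their first treatment with the study drug".

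**Counts.** Section 8.2 sets a Simon two-stage design for each arm. Ten patients are accrued, the arm stops on 0 or 1 responses, and otherwise 19 more are accrued for a total of 29. The stated alpha is 0.0471 and the stated power 80.5%, for 10% against 30%. Section 3.1 gives the same sizes for the two ER+ arms. The six-patient look for dose modification counts patients enrolled. None of these places mentions replacement.

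**The concern.** A patient whose vorinostat is held in cycle 1 or 2 has been dosed and, in Arms A and B, randomised. Section 8.3 therefore keeps that patient in both the efficacy and the safety analysis, while the footnote calls for someone else to be assessed instead, for both purposes.

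The trigger is an on-treatment event, and where the footnote sits it is a toxicity. Substituting patients on that basis would remove people with toxicity from a trial in which toxicity is a primary endpoint. If these patients also respond less often, ORR among the remaining patients would be too high.

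The stage counts matter separately. The error rates of a two-stage design depend on who makes up the 10 and the 29. If it is unsettled whether a replaced patient keeps a slot, then both the stopping decision and the final decision are left open to a choice that could be made after outcomes are known.

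**Working it through.** **Inputs.** From section 8.2: null rate 10%, alternative 30%, n1 = 10, stop on 0 or 1, n = 29, alpha 0.0471, power 80.5%. From section 8.3.2: Agresti-Coull 95% lower bound above 10%. The share replaced, q, is an assumption (2%, 5%, 10%), because the documents give none. The expected number replaced while filling 29 slots is 29q/(1−q), or about 0.6, 1.5 and 3.2 patients.

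**Step 1: the plan's own figures.** With X1 responses in stage 1 and X in total, the chance of a positive arm is P(X1 ≥ 2 and X ≥ c), that is, the sum over x = 2 to 10 of Bin(x; 10, p) × P(Bin(19, p) ≥ c − x). The final cut-off c is not printed.
- c = 6: 0.0471 at p = 0.10 and 0.8051 at p = 0.30. This reproduces the stated design.
- c = 7: 0.0177 and 0.7389.

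**Step 2: the cut-off under the printed rule.** The lower bound is p̃ − 1.96 × √(p̃(1−p̃)/ñ), with ñ = n + 1.96² and p̃ = (x + 1.96²/2)/ñ.
- 6/29: 0.0949, fails.
- 7/29: 0.1195, passes.

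The printed rule therefore needs 7/29 and starts from alpha 1.8%. The cut-off that matches the stated design needs 6/29 and starts from 4.7%. Both are carried through.

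**Step 3: substitution.** Worst case: every replaced patient would have been a non-responder. A true rate p then appears in the filled slots as p/(1−q).

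| q | true 10% reads as | true 30% reads as | alpha, 7/29 | alpha, 6/29 |
|---|---|---|---|---|
| 0 | 10.0% | 30.0% | 0.0177 | 0.0471 |
| 2% | 10.2% | 30.6% | 0.0196 | 0.0511 |
| 5% | 10.5% | 31.6% | 0.0228 | 0.0578 |
| 10% | 11.1% | 33.3% | 0.0297 | 0.0712 |

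Milder case: replaced patients respond at 5%, so the slot rate is (0.10 − 0.05q)/(1−q). For q = 2%, 5% and 10%, alpha is 0.0186, 0.0201 and 0.0231 at 7/29, and 0.0491, 0.0523 and 0.0584 at 6/29.

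Under the printed rule, the worst case reaches 0.0471 only at about q = 18.5%.

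**Step 4: addition.** Keep the replaced patient and add another. With one addition in stage 1 and one later, the arm is 11 then 31, all responding at 10%.
- Printed rule: 6/31 has lower bound 0.0882 and 7/31 has 0.1111, so 7 responses are still needed. P(X1 ≥ 2 of 11 and X ≥ 7 of 31) = 0.0255.
- Six-response cut-off: P(X1 ≥ 2 of 11 and X ≥ 6 of 31) = 0.0633.

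Addition also strains the stated maximum. Three arms of 29 make 3 × 29 = 87, the upper limit in section 3.2, which leaves no room for extra patients if all arms go to stage 2.

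**The case against.** The strongest reply is that to replace is not to exclude. A sponsor may accrue a further patient and leave the first in the intention-to-treat and safety sets. On that reading section 8.3 is intact. Section 8.3 is also explicit and is where an analyst would look; a footnote in a dose-modification table is weak evidence of a rival analysis plan. This stands in part: it is too strong to say that the plan flatly contradicts itself. But the footnote names toxicity and efficacy assessments as what the replacement is for, which leans towards substitution. The additive reading moves the difficulty to the counts without settling it.

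The second reply concerns size, and it largely stands. Under the only final rule that is printed, alpha stays below the stated 4.71% throughout the 2–10% range. The larger figures need a cut-off that the plan does not print, although it is the one that reproduces the stated design. Sections 4.1.2 and 5.1.1.1 list vorinostat's dose-limiting toxicities as anorexia, dehydration, diarrhea and fatigue, not neutropenia, so nothing suggests that long early neutropenia holds would be common. The footnote's own words are not confined to neutropenia, however. The narrow trigger is inferred from where the marker sits.

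A reader might also infer that replacement shrinks the denominator, so that a count failing at 29 would pass. That does not follow: replacement refills the slot and the denominator stays at 29.

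Two neighbouring questions are separate and are not relied on here. One is the response-evaluable definition in section 7.1.2 ("have received at least one cycle of therapy, and have had their disease re-evaluated will be considered evaluable for response"), which can be read alongside section 8.3.2. The other is whether Arm C is randomised.

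**Conclusion.** The point holds as an unreconciled rule. Substitution conflicts with sections 8.3.1 to 8.3.3, 7.1.2 and 7.4. Addition departs from the 10 and 29 of section 8.2. The documents do not choose between the two or say which patients count.

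Substitution can understate toxicity and, if replaced patients respond less often, overstate ORR. The worst-case effect at 2–10% replaced is alpha of 2.0–3.0% under the printed rule, or 5.1–7.1% at 6/29. Addition of two patients gives 2.5% or 6.3%. These figures rest on an assumed replacement share and, for substitution, on all replaced patients being non-responders. The addition figures assume the same response rate for everyone.

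A reader might infer that the trial's type I error is seriously inflated. The documents do not support that: they give no replacement rate, and under the printed rule the design has room to spare. The effect is probably small. It is still worth correcting, because one or two patients can decide a stage in arms of this size.

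**What to change.** - State that section 8.3 governs the analysis sets. Remove the footnote's replacement phrase as an analysis rule, so that patients with a long early delay stay in the efficacy and safety sets.
- Apply the stage rules to the first 10 and first 29 patients randomised in Arms A and B, or enrolled in Arm C. Count those without stable disease or better at 24 weeks as non-responders, as section 8.3.2 already implies.
- Settle this before the outcomes of any delayed patients are known.

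The clinical handling of long delays is for the sponsor and is not part of this point; the passages only need to be reconciled.

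The cost is protocol and SAP wording, with no extra patients. The downside is a slightly lower observed ORR, because delayed patients without a qualifying 24-week status count against the arm. In return, the counts of 10 and 29 behind the stated alpha and power are kept.
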